had occurred in a more severe form.

Hospitalization or Prolongation of Hospitalization An event that results in an admission to the hospital for any length of time or prolongs the subject's hospital stay. This does not include an emergency room visit or admission to an outpatient facility.

**Congenital Anomaly** An anomaly detected at or after birth, or any anomaly that results in

fetal loss.

Persistent or Significant Disability/Incapacity

An event that results in a condition that substantially interferes with the activities of daily living of a study subject. Disability is not intended to include experiences of relatively minor medical significance such as headache, nausea, vomiting, diarrhea, influenza, and accidental trauma (e.g., sprained ankle).

Important Medical Event Requiring Medical or Surgical Intervention to Prevent Serious Outcome An important medical event that may not be immediately lifethreatening or result in death or hospitalization, but based on medical judgment may jeopardize the subject and may require medical or surgical intervention to prevent any of the outcomes listed above (i.e., death of subject, life threatening, hospitalization, prolongation of hospitalization, congenital anomaly, or persistent or significant disability/incapacity). Additionally, any elective or spontaneous abortion or stillbirth is considered an important medical event. Examples of such events include allergic bronchospasm requiring intensive treatment in an emergency room or at home, blood dyscrasias or convulsions that do not result in inpatient hospitalization, or the development of drug dependency or

All AEs reported from the time of study drug administration until 30 days after discontinuation of study drug administration will be collected, whether solicited or spontaneously reported by the subject. In addition, SAEs and protocol-related nonserious AEs will be collected from the time the subject signs the study-specific informed consent.

drug abuse.

AbbVie will be responsible for Suspected Unexpected Serious Adverse Reactions (SUSAR) reporting for the Investigational Medicinal Product (IMP) in accordance with global and local requirements.

Adverse events will be monitored throughout the study to identify any of special interest that may indicate a trend or risk to subjects.

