## 4 SAFETY MANUAL

## 4.1 Methods and Timing of Safety Assessment

All serious adverse events (SAEs) as well as protocol-related nonserious AEs (e.g., occurrence during Screening) will be collected from the time the subject signed the study-specific informed consent until study drug administration. From the time of study drug administration until 30 days after discontinuation of study treatment, all AEs and SAEs will be collected whether solicited or spontaneously reported by the subject. After 30 days following completion of study treatment and throughout the Post-Treatment Period, all spontaneously reported SAEs will be collected (nonserious AEs will not be collected).

Adverse events of special interest, such as elevated liver transaminases, decreased BMD/ bone fractures, and all mood- and depression-related events, will require additional information, to be collected in the EDC system.

Adverse event information will be collected as shown in Figure 2.

SAEs and Protocol-Related SAEs and Nonserious AEs Nonserious AEs Elicited and/or Spontaneously Reported

Consent Study Drug Study Drug 30 Days After Signed Start Stopped Study Drug Stopped

Figure 2. Adverse Event Collection

AE = adverse event; SAE = serious adverse event

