# 4.2 Recording Data and Analyses of Safety Findings

Adverse events will be coded using the Medical Dictionary for Regulatory Activities (MedDRA). The number and percentage of subjects with treatment-emergent AEs (i.e., any event that begins or worsens in severity after initiation of study drug through 30 days post-study drug dosing) will be tabulated by primary MedDRA System Organ Class (SOC) and preferred term (PT) and compared between arms using Fisher's exact test. The tabulation of the number of subjects with treatment-emergent AEs by severity grade and relationship to study drug also will be provided. Subjects reporting more than 1 AE for a given

MedDRA preferred term will be counted only once for that term using the most severe grade according to the severity grade table and the most related according to the relationship to study drug tables. Subjects reporting more than 1 type of event within an SOC will be counted only once for that SOC.

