6.0 Study Drug Duration

For the Safety Analysis Set, duration of treatment will be summarized for each treatment group and for all investigational study drug dose groups combined. Duration of treatment is defined for each subject as last dose date minus first dose date + 1. Duration of treatment will be summarized using the number of subjects treated, mean, standard deviation, median, minimum and maximum. In addition, the number and percentage of subjects in each treatment duration interval (1 – 28, 29 – 56, 57 – 84, 85 – 112, 113 – 140, 141 – 168, and > 168 days) will be summarized.

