9.2 Adverse Events

Adverse events (AEs) will be summarized and presented using primary MedDRA System Organ Classes (SOCs) and preferred terms (PTs) according to the version of the MedDRA coding dictionary used for the study at the time of database lock. The actual version of the MedDRA coding dictionary used will be noted in the AE tables and in the clinical study report. Specific adverse events will be counted once for each subject for calculating percentages, unless stated otherwise. In addition, if the same adverse event occurs multiple times within a subject, the highest severity and level of relationship to investigational product will be reported.

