9.2.1 Treatment-Emergent Adverse Events

Treatment-emergent AEs are defined as any AE with the onset that is after the first dose of study drug. Events where the onset date is the same as the study drug start date are assumed to be treatment-emergent. All treatment-emergent AEs will be summarized overall, as well as by primary MedDRA SOC and Preferred Term. The SOCs will be presented in alphabetical order, and the PTs will be presented in alphabetical order within each SOC.

The number and percentage of subjects experiencing treatment-emergent AEs will be summarized.

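### If early stopping differs between arms, crude AE percentages understate mainly later nonserious events in the arm observed for less time; an exposure-adjusted rate beside them is a cheap improvement.

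*SAP*

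**What the plan says.** **How AEs are counted.** SAP 9.2.1 states: "The number and percentage of subjects experiencing treatment-emergent AEs will be summarized". SAP 9.2 adds: "Specific adverse events will be counted once for each subject for calculating percentages, unless stated otherwise". The overview (9.2.2), the SOC and PT tables (9.2.3, 9.2.4) and the events of special interest (9.2.5) follow the same pattern. None uses person-time or time to first event.

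**How they are compared.** SAP 9.2 names no test for AEs. The comparison is in Operations Manual 4.2 (Protocol Appendix F), where treatment-emergent AEs are tabulated by SOC and "preferred term (PT) and compared between arms using" Fisher's exact test.

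**How long they are collected.** Protocol 6.1: "All AEs reported from the time of study drug administration until 30 days after discontinuation of study drug administration will be collected". Operations Manual 4.1 then separates serious from nonserious events: "After 30 days following completion of study treatment and throughout the Post-Treatment Period, all spontaneously reported SAEs will be collected", but "nonserious AEs will not be collected".

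**Which events count as treatment-emergent.** Operations Manual 4.2 closes the window: "any event that begins or worsens in severity after initiation of study drug through 30 days post-study drug dosing". SAP 9.2.1 starts the window at the first dose and gives it no end.

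**What is known about exposure.** SAP 6.0: "Duration of treatment is defined for each subject as last dose date minus first dose date + 1". Duration is summarised by arm, and SAP 5.0 tabulates discontinuation by reason. Neither feeds into the AE tables.

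**The concern.** For nonserious events, observation time is tied to time on drug. A woman who stops early and one who completes each add one to the denominator, although the first had far less time in which an event could be recorded. Shorter observation can only lower a crude percentage relative to full follow-up. If arms differ in how many women stop or how early, their percentages therefore do not describe the same length of observation.

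What is at stake is the description of tolerability across five regimens from 50 to 300 mg per day. A true excess of later nonserious events could be partly hidden in an arm that loses more observation time. The SAP already allows for unequal exposure elsewhere: it analyses bleeding episodes and ovulations per month of treatment (8.5.3, 8.5.4). The AE section has no counterpart.

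**Working it through.** The plan gives no AE rate, dropout rate or expected exposure, so it has no figure of its own to reproduce here. Its one design figure, power of at least 85% for the primary endpoint, does not enter.

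**Inputs from the documents.** Treatment lasts 24 weeks (168 days) and AE collection runs 30 days beyond the last dose, so a completer is at risk for 168 + 30 = 198 days, about 28 weeks. Arms are 20 per elagolix group and 30 on placebo (SAP 2.4). AE incidence, stopping rates and stopping times below are all assumed.

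**Step 1: time at risk.** A woman stopping on day 28, 56 or 84 contributes 58, 86 or 114 days, against 198.

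**Step 2: shift when the true hazards are equal and stopping is unrelated to AEs.** Let I be the incidence over 28 weeks, h = −ln(1 − I)/28, and P(t) = 1 − exp(−h·t) the incidence in a stopper with t weeks at risk. With a fraction d stopping, the arm's percentage is (1 − d)·I + d·P(t). The difference between two arms is −(d₁ − d₀)·(I − P(t)).

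For I = 0.5, h = 0.02476, P(8) = 0.180 and P(12) = 0.257. With 30% versus 10% stopping, the shift is −0.20 × 0.320 = −6.4 points or −0.20 × 0.243 = −4.9 points. In points:

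| Incidence | Stopping | 8 weeks at risk | 12 weeks at risk |
|---|---|---|---|
| 50% | 30% vs 10% | −6.4 | −4.9 |
| 50% | 50% vs 15% | −11.2 | −8.5 |
| 30% | 30% vs 10% | −4.1 | −3.2 |
| 50% | 5-point gap | −1.6 | −1.2 |
| any | balanced in amount and timing | 0 | 0 |

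If stopping is spread evenly over the 24 weeks, each stopper having 30 days (4.29 weeks) more, the mean stopper incidence at I = 0.5 is 1 − exp(−4.29h)·(1 − exp(−24h))/(24h) = 1 − 0.899 × 0.754 = 0.322. With 30% versus 10% stopping the shift is −0.20 × 0.178 = −3.6 points.

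In an arm of 20, 3.6 to 6.4 points is 0.7 to 1.3 women. The standard error at 50% is √(0.25/20 + 0.25/30) = 14.4 points.

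**Step 3: stopping because of an AE.** Assume 40% placebo incidence over 198 days and 10% unrelated stopping on day 56 in both arms, with a further 30% on active stopping for an AE that is itself counted. A day-56 stopper has incidence 0.199. Active any-AE is 0.1 × 0.199 + 0.30 + 0.6 × 0.40 = 56.0%. With full follow-up for everyone else it would be 0.30 + 0.7 × 0.40 = 58%. Placebo reads 0.1 × 0.199 + 0.9 × 0.40 = 38.0%. The poorly tolerated arm still looks clearly worse.

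**Step 4: late-onset terms.** Take an event that arises only after day 86, with true risk 20% and stopping on day 56. It reads 0.20 × 0.6 = 12% with 40% stoppers and 0.20 × 0.9 = 18% with 10% stoppers.

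**Step 5: what a rate recovers, and where it misleads.** Assume 40% placebo incidence over 198 days, a true hazard ratio of 1.25, and 40% versus 10% stopping on day 56 unrelated to AEs. Both crude percentages are 38.0%; with full follow-up they would be 47.2% and 40.0%. Under a constant hazard, first events per 100 subject-months of 28 days estimate 0.5108/198 × 2,800 = 7.2 on placebo and 7.2 × 1.25 = 9.0 on active, which recovers the ratio.

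Now suppose instead that a rare event occurs only before anyone stops, with equal risk in both arms. The percentages are correct. Mean time at risk, however, is 0.4 × 86 + 0.6 × 198 = 153.2 days against 0.1 × 86 + 0.9 × 198 = 186.8 days. The rate then suggests a false ratio of about 186.8/153.2 = 1.22.

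**The case against.** The strongest objection is that the effect is conditional and small. The documents give no dropout rates, and greater stopping at higher doses is conjecture; placebo could lose more women instead. A gap of 20 points with every stopper leaving early is a demanding scenario, and even then the shift is well inside the random error of a proof-of-concept study that disclaims Type I error control (SAP 10.0). This stands, and it limits the weight of the point.

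A reader might also infer that the worst-tolerated dose will look safer than it is across the board. The documents do not support that. A woman who stops for an AE is counted under any AE and under AEs leading to discontinuation (SAP 9.2.2, 9.2.4), and Step 3 shows how little is lost. Duration by arm in 28-day bands (SAP 6.0) and reasons for stopping (SAP 5.0) would also show an imbalance, although they do not adjust for it.

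Nor does all safety observation end at 30 days. Spontaneously reported SAEs are still collected. Women who stop drug are asked to keep attending visits unless they withdraw consent (Protocol 5.6), and the C-SSRS is summarised at each scheduled treatment-period assessment (SAP 9.5.1). Suicidality can therefore be captured later, but other nonserious mood events are not.

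**Conclusion.** The point holds in conditional form. AEs are summarised and compared as percentages of subjects, nonserious collection depends on time on drug, and no person-time measure is planned. If stopping differs between arms in amount or timing, the arm with less time at risk is understated, mainly for later-onset and less frequent nonserious terms.

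Under the assumed 50% incidence and 30% versus 10% stopping unrelated to AEs, the understatement is about 3.6 points with evenly spread stopping and 6.4 points if every stopper has 8 weeks at risk. It vanishes if stopping is balanced. Against a standard error of about 14 points, this affects how the dose and safety pattern is described more than it affects any test.

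It would go too far to conclude that a rate should be the sole basis for statements between doses. Step 5 shows that percentages mislead in one setting and rates in another. This is a worthwhile, inexpensive improvement and does not invalidate the safety analysis.

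**What to change.** - Keep n (%) in all AE tables.
- In SAP 9.2.2 and 9.2.5, add beside it an exposure-adjusted incidence rate for each arm, the total active group and placebo: subjects with a first event per 100 subject-months. Time at risk runs from first dose to the earliest of first event, last dose + 30 days, or last contact.
- State that rates are read together with the percentages and with the duration and discontinuation tables of SAP 6.0 and 5.0.
- Use one window for numerator and denominator by reconciling the open-ended definition in SAP 9.2.1 with the 30-day limit in Operations Manual 4.2. As written, an SAE on day 150 in a woman who stopped on day 56 is treatment-emergent under the SAP but not under the Operations Manual, whose window closes on day 86 (56 + 30).

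**Cost.** SAP wording, one derived variable and an extra column. First and last dose dates are already needed for SAP 6.0, and no new data are collected.

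**Downside.** The rate assumes a roughly constant hazard, can overstate risk in an arm with many early stoppers if AEs cluster early, and is unstable for rare terms with 20 women per arm.

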9.2.2 Adverse Event Overview

An overview of AEs will be presented consisting of the number and percentage of subjects experiencing at least one event for each of the following AE categories:

- Any treatment-emergent AE
- Any treatment-emergent AE related to study drug according to the investigator
- Any severe treatment-emergent AE

- Any serious treatment-emergent AE
- Any treatment-emergent AE leading to discontinuation of study drug
- Any treatment-emergent AE of special interest as specified in [Appendix A](#)
- Any treatment-emergent AE leading to death
- All deaths

9.2.3 Treatment-Emergent Adverse Events by SOC and PT

Treatment-emergent adverse events will be summarized by SOC and PT; by maximum relationship to study drug as assessed by the investigator (e.g., reasonable possibility or no reasonable possibility) and SOC and PT; by maximum severity and SOC and PT; and by subject number and SOC and PT. Specific adverse events will be counted once for each subject for calculating percentages, unless stated otherwise. In addition, if the same adverse event occurs multiple times within a subject, the highest severity and level of relationship to investigational product will be reported.

In addition, treatment-emergent adverse events will be summarized by PT and sorted by decreasing frequency for the total active group.

9.2.4 Deaths, Other Serious Adverse Events, and Adverse Events Leading to Study Drug Discontinuation

The number and percentage of subjects experiencing the following categories will be tabulated according to the primary MedDRA SOC and PT. In addition, listing of subjects experiencing the following categories will be generated.

- Treatment-emergent SAEs
- Treatment-emergent AEs leading to discontinuation of study drug
- Treatment-emergent AEs leading to death

9.2.5 Adverse Events of Special Interest

Adverse events of special interest will be summarized by SOC and PT and will be based on standardized or company MedDRA queries (SMQs or CMQs), or based on adjudication results. Adverse events of special interest are categorized as follows:

- Elevated hepatic transaminases
- BMD decrease/fractures
- Mood and depression-related events

Detailed information about the search criteria are provided in [Appendix A](#).

9.3 Analysis of Laboratory Data

Data collected from central and local laboratories, including additional laboratory testing due to an SAE, will be used in all analyses, except for Baseline where SAE-related laboratory assessments on or before the first dose of study drug will be excluded. The clinical laboratory tests defined in the protocol operations manual (e.g., hematology and clinical chemistry) will be summarized.

Each laboratory variable will be summarized for all time points (starting with Baseline) with the number of non-missing observations, mean and standard deviation, median, minimum and maximum. Mean change from baseline to each applicable post-baseline visit will be summarized for selected laboratory variables, with the number of observations, baseline mean, and visit mean. The change from baseline mean, standard error, and 95% confidence interval will be presented for the mean change from baseline within each treatment group and difference between each elagolix group and placebo. Selected laboratory variables are lipid variables, liver variables (alkaline phosphatase, ALT, AST, bilirubin), hemoglobin, hematocrit, platelet count, and red blood cell (RBC) count.

Changes in laboratory parameters will be tabulated using shift tables either by NCI CTC criteria or categorized as low, normal, or high based on the normal ranges of the

laboratory used for each sample. A shift table from baseline either to the worse value (based on NCI CTC criteria) during treatment or to minimum and maximum value (based on normal range), will be created. A similar shift table will be provided to summarize shifts from baseline to the final post-baseline value.

Laboratory abnormalities meeting CTCAE criteria grade 3 and 4 will be summarized.

The number and percentage of subjects meeting the following criteria will be summarized at Baseline and each relevant visit by treatment group in the Treatment Period:

- Total cholesterol: ≤ 300 , $> 300 - \leq 400$, $> 400 - \leq 500$, and > 500 mg/dL
- HDL-C: < 40 and ≥ 40 mg/dL
- LDL-C: < 130 , $\geq 130 - < 160$, $\geq 160 - < 190$, and ≥ 190 mg/dL
- TG: ≤ 150 , $> 150 - \leq 300$, $> 300 - \leq 500$, $> 500 - \leq 1000$, and > 1000 mg/dL

In addition, the number and percentage of subjects who have potentially clinically significant (PCS) lipid values meeting the following criteria any time during the Treatment Period will be summarized by treatment group: Listings will be provided to summarize subject-level laboratory data for subjects meeting PCS criteria.

- Total cholesterol > 200 mg/dL
- LDL-C > 130 mg/dL
- LDL-C > 160 mg/dL
- HDL-C < 40 mg/dL
- TG > 150 mg/dL

The number and percentage of subjects in each treatment group with maximum on treatment laboratory values meeting the following criteria compared to the upper limit of normal (ULN) will be summarized by treatment group to assess potential hepatotoxicity.

- ALT $\geq 3 \times$ ULN and total bilirubin $\geq 2 \times$ ULN
- AST $\geq 3 \times$ ULN and total bilirubin $\geq 2 \times$ ULN

- ALT and AST $\geq 3 \times$ ULN and total bilirubin $\geq 2 \times$ ULN
- ALT $\geq 3 \times$ ULN and total bilirubin $< 2 \times$ ULN
- AST $\geq 3 \times$ ULN and total bilirubin $< 2 \times$ ULN
- ALT and AST $\geq 3 \times$ ULN and total bilirubin $< 2 \times$ ULN
- ALT $\geq 3 \times$ ULN and total bilirubin $\geq 1.5 \times$ ULN
- AST $\geq 3 \times$ ULN and total bilirubin $\geq 1.5 \times$ ULN
- ALT and AST $\geq 3 \times$ ULN and total bilirubin $\geq 1.5 \times$ ULN
- ALT $\geq 3 \times$ ULN, $\geq 5 \times$ ULN, $\geq 10 \times$ ULN, $\geq 20 \times$ ULN
- AST $\geq 3 \times$ ULN, $\geq 5 \times$ ULN, $\geq 10 \times$ ULN, $\geq 20 \times$ ULN
- Total bilirubin $\geq 1.5 \times$ ULN, $\geq 2.0 \times$ ULN

The maximum ratio relative to the ULN is used to determine if subjects met the criteria listed above. The ALT, AST, and total bilirubin values do not need to be concurrent in order to meet the defined criteria. For ALT, AST, and total bilirubin, a subject is counted if the post-baseline laboratory value during the Treatment Period meets the above criteria regardless of Baseline laboratory value (i.e., the post-baseline laboratory value does not need to be worse than Baseline laboratory value).

A listing of all ALT, AST, total bilirubin, and alkaline phosphatase values will be provided for each subject who met any of the criteria defined above.

The following plots will be generated: peak AST vs. peak bilirubin; peak ALT vs. peak bilirubin.

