2.4 Sample Size Determination

The planned total sample size is 130 subjects: 20 subjects per elagolix treatment group and 30 subjects assigned to placebo.

The sample size will provide at least 85% power to detect a difference between each elagolix group and the placebo group in the proportion of menstrual cycle responders based on a Pearson Chi-square test, assuming response rates of 10% for the placebo group and 50% for the elagolix group with 2-sided $\alpha = 0.05$. The above sample size was calculated using nQuery advisor 7.0.

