8.5.5 Change from baseline for other clinical efficacy endpoints

Change from baseline to each scheduled assessment for the following endpoints will be analyzed: acne measured with total lesion count and investigator global assessment of acne, hirsutism measured with Ferriman–Gallwey (FG) score, metabolic features (Hb A1c, fasting insulin/glucose, body mass index (BMI), lipids [LDL cholesterol, HDL cholesterol, total cholesterol, triglycerides], waist circumference), ovarian volume, and endpoints related to subject's quality of life (PCOSQ [emotions, body hair, weight, infertility problems, and menstrual problems], and MBQ). The analysis will be based on

one-way ANCOVA with treatment group as the main effect, and baseline FG score (< 8 , ≥ 8), baseline normal/obese status ($\text{BMI} < 30$, ≥ 30), and baseline value of the corresponding endpoint being analyzed as the covariates.

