9.0 Safety Analyses

9.1 General Considerations

Safety analyses will be carried out using Safety Analysis Set. All safety analyses will be based on observed data. Unless otherwise specified, missing data will not be imputed.

For continuous variables, when the analyses of change and/or percent change from Baseline to post-baseline visit(s) are performed, the within-group change from Baseline to each relevant visit will be summarized by treatment group with the mean, SE, and 95% CIs. The between-group differences will be summarized with the mean, SE, 95% CIs, and P value when applicable. P value will be compared to an alpha level of 0.05. At each post-baseline visit, the Baseline mean and post-baseline visit mean will be calculated for all subjects with baseline and post-baseline value at that visit by treatment group.

Categorical data will be summarized by number and percentage of subjects by treatment group.

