9.5.2 Bone Mineral Density

All analyses and summaries of bone mineral density (BMD) will be performed for each segment, i.e., femoral neck, lumbar spine, and total hip. For subjects who had a right-side scan performed (rare instances), their data for right femoral neck and right femoral total hip will be included in the analysis with the data for the left femoral neck and left total hip, respectively (available for the majority of subjects). If more than one scan is reported for an anatomical segment within an analysis window, the worse (the lower value) of the multiple measurements will be used for analysis for each anatomical segment. The analyses below will exclude subjects who switch machine manufacturer types between baseline and post-baseline.

A continuous summary of BMD at Baseline and Month 6 will be provided by treatment group. This summary will include the mean, SD, median, minimum, and maximum.

The analysis of percent change from baseline in BMD during the Treatment Period will be based on an ANCOVA model with treatment as the main effect and baseline value of

corresponding parameter as a covariate. Each elagolix group will be compared to placebo.

The number and percentage of subjects with percent change from Baseline to Month 6 during the Treatment Period in mutually exclusive categories of BMD decrease: $\leq 0\%$, $> 0\% - \leq 1.5\%$, $> 1.5\% - \leq 3\%$, $> 3\% - \leq 5\%$, $> 5\% - < 8\%$, and $\geq 8\%$ will be summarized by treatment group. The comparison between each elagolix group and placebo will be made using Fisher's exact test.

A listing of subjects with BMD decrease from baseline $\geq 8\%$ will be provided.

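### SAP 9.3 and 9.4 specify no baseline adjustment for between-arm differences in laboratory and blood-pressure change, which costs precision when the baseline-to-visit correlation is low to moderate

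*SAP*

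**What the plan says.** SAP 9.3 covers selected laboratory variables: the lipids, four liver tests and four blood-count variables. For these a "95% confidence interval will be presented for the mean change from baseline within each treatment group and difference between each elagolix group and placebo". SAP 9.4 has the same sentence for vital sign variables, which it defines as sitting systolic and diastolic pressure. The general safety rule in SAP 9.1 asks for a mean, SE and 95% CI for between-group differences, with a P value where applicable, and adds that the "P value will be compared to an alpha level of 0.05". None of these sections names a model, a baseline covariate or a stratum.

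Elsewhere the SAP states its adjustment. BMD in 9.5.2 uses an "ANCOVA model with treatment as the main effect and baseline value of" the same parameter as covariate. SAP 8.5.5 analyses LDL, HDL, total cholesterol and triglycerides by ANCOVA, with the FG category, the BMI category and the "baseline value of the corresponding endpoint being analyzed as the covariates".

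The planned arms in SAP 2.4 are "20 subjects per elagolix treatment group and 30 subjects" on placebo.

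**The concern.** The baseline value is collected for every variable concerned, and the SAP uses it for BMD and for the efficacy endpoints. Leaving it out of 9.3 and 9.4 gives up precision where the arms are small. A raw change difference also moves against any chance baseline imbalance: if an elagolix arm starts higher than placebo, regression to the mean makes its change look lower.

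The liver tests matter most. Elevated hepatic transaminases are an adverse event of special interest, eligibility admits ALT and AST up to just under 3 times the upper limit of the reference range, and no section gives these variables a baseline-adjusted comparison. Blood counts and blood pressure have the same gap. The lipids will appear twice, adjusted in 8.5.5 and apparently raw in 9.3, with nothing in the SAP to relate the two results.

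**Working it through.** **Step 1. The plan's own figure.** SAP 2.4 claims "at least 85% power to detect a difference between each elagolix group and the placebo group". The calculation there uses a Pearson chi-square test on responder rates of 10% (placebo) and 50% (elagolix), two-sided at 5%.
- Pooled rate: (30 × 0.10 + 20 × 0.50)/50 = 0.26.
- SE under the null: √(0.26 × 0.74 × (1/30 + 1/20)) = 0.1266.
- SE under the alternative: √(0.09/30 + 0.25/20) = 0.1245.
- z = (0.40 − 1.96 × 0.1266)/0.1245 = 1.22, so power is 88.9%.

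The stated figure is reproduced. It concerns the primary endpoint and confirms the 20-versus-30 layout used below; nothing in this point alters it.

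**Step 2. Inputs.** Arms of 20 and 30 (SAP 2.4) and 95% intervals (SAP 9.1, 9.3, 9.4). The baseline-to-visit correlation ρ and the SDs are not in the documents. I assume equal SDs σ at baseline and follow-up, a linear relation, full arms at the visit, and ρ from 0.3 to 0.98.

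**Step 3. Interval width.**
- Variance of a change score: 2σ²(1 − ρ).
- Residual variance after ANCOVA: σ²(1 − ρ²).
- Large-sample width ratio, ANCOVA to raw change: √((1 + ρ)/2).
- With N = 50 and k covariates, multiply by √(1 + k/(N − 3 − k)) and by the ratio of t quantiles on N − 2 − k and N − 2 degrees of freedom.
- Example, ρ = 0.5 and k = 1: 0.866 × √(1 + 1/46) × 1.001 = 0.876, about 12% narrower.

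**Step 4. Chance imbalance.**
- SD of the baseline difference between arms: √(1/20 + 1/30) = 0.289 SD.
- Shift in the raw change difference: (1 − ρ) × imbalance.
- SE of the raw difference: √(2(1 − ρ)) × 0.289 SD. A 1-SD imbalance therefore shifts the result by √((1 − ρ)/2) standard errors.

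| ρ (assumed) | Large-sample ratio | Pairwise, baseline only | Pairwise, baseline + two non-prognostic strata | Six-arm, baseline only / + strata | Shift from a 1-SD imbalance |
|---|---|---|---|---|---|
| 0.3 | 0.806 | 0.815 | 0.835 | 0.810 / 0.816 | 0.202 SD = 0.59 SE |
| 0.5 | 0.866 | 0.876 | 0.897 | 0.870 / 0.877 | 0.144 SD = 0.50 SE |
| 0.7 | 0.922 | 0.932 | 0.955 | 0.926 / 0.934 | 0.087 SD = 0.39 SE |
| 0.8 | 0.949 | 0.959 | 0.982 | 0.953 / 0.961 | 0.058 SD = 0.32 SE |
| 0.9 | 0.975 | 0.986 | 1.009 | 0.979 / 0.987 | 0.029 SD = 0.22 SE |
| 0.95 | 0.987 | 0.999 | 1.022 | 0.992 / 1.000 | 0.014 SD = 0.16 SE |
| 0.98 | 0.995 | 1.006 | 1.030 | 0.999 / 1.008 | 0.006 SD = 0.10 SE |

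The six-arm column (N = 130) is relative to an unadjusted six-arm interval.

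**Step 5. Check.** In 4,000 simulated 20-versus-30 comparisons at each of ρ = 0.5, 0.7, 0.9 and 0.98, the pairwise baseline-only ratios were 0.877, 0.933, 0.985 and 1.005. With two irrelevant strata they were 0.896, 0.955, 1.007 and 1.028. Both sets agree with the formula.

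**The case against.** The strongest reply is that nothing here is invalid. Under randomisation the raw difference in change is unbiased, and chance imbalance is already in its standard error. An imbalance above 0.3 SD arises in about 30% of 20-versus-30 comparisons. At ρ = 0.6 an imbalance of 0.3 SD shifts the raw difference by 0.4 × 0.3 = 0.12 SD, against an SE of √0.8 × 0.289 = 0.258 SD, or about 0.46 SE. This stands. A reader might infer that safety signals will be created or hidden; the arithmetic does not support that.

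Mean change is also not the only safety screen. SAP 9.3 adds shift tables, grade 3 and 4 counts, multiples of the upper limit of normal, combined transaminase and bilirubin criteria, plots and listings. SAP 9.4 adds blood-pressure criteria, most of which combine a limit with a change from baseline. Baseline and visit means are shown by arm, so an imbalance would be visible. This stands too and limits the consequence.

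Three wider readings are tempting and should be resisted:
- **Weight.** A reader might extend the point to weight change. The mean-change sentence in 9.4 names vital sign variables only, and weight is not one of them. It gets descriptive summaries and threshold categories, and BMI has an adjusted analysis in 8.5.5.
- **Lipids.** A reader might infer that no adjusted lipid comparison will exist. SAP 8.5.5 provides one.
- **Strata.** A reader might hold that the FG and BMI strata must be added throughout, including to the BMD model. Randomisation already limits imbalance in those categories, and the documents do not show that they predict the safety variables.

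Finally, the absence of adjustment is inferred from silence. The explicit models in 8.5.5 and 9.5.2 make it the plain reading, and if the sponsor intends otherwise the text still needs the method named.

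**Conclusion.** The point holds as a modest matter of precision and specification. SAP 9.3 and 9.4 do not use a baseline value that is already collected, mainly for liver tests, blood counts and blood pressure. On the assumptions in step 2, baseline ANCOVA narrows the pairwise 95% interval by about 12%, 7%, 4% and 1% at ρ = 0.5, 0.7, 0.8 and 0.9. It gives nothing from about 0.95. It also removes the (1 − ρ) × imbalance shift, provided the relation with baseline is close to linear.

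It would be wrong to conclude that the planned intervals are wider than necessary for every variable: that depends on ρ, which the documents do not give. The primary analysis and its power are unaffected.

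**What to change.** In SAP 9.3 and 9.4, estimate each between-group difference by ANCOVA on change, with treatment and the baseline value of the variable. Preferably fit one model to all six arms. The FG (<8, ≥8) and BMI (<30, ≥30) strata may be included. Report the adjusted differences with 95% CIs beside the raw means already planned.

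Add a sentence relating the two sets of lipid results. SAP 8.5.5 uses the full analysis set by randomised arm with 90% intervals (SAP 8.1); SAP 9.3 uses the safety set by treatment received with 95% intervals. They will therefore not match exactly even once both are adjusted. Adding the strata to the BMD ANCOVA in 9.5.2 is optional.

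The cost is SAP wording and minor programming, with no new data. The only statistical downside is for very highly correlated variables (ρ of about 0.9 or more): if non-prognostic strata are added in pairwise models, the interval can be 1% to 3% wider. The six-arm model largely avoids this (ratios of 0.99 to 1.01 over the same range).
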